Reference Drug	Aranesp [®] (INN: darbepoetin alfa, Amgen Europe B.V., the Netherlands), solution for injection
Study Purpose and Objectives	
The purpose of the study is to confirm the equivalent pharmacokinetics, pharmacodynamics, safety, and tolerability of multiple IV injections of BCD-066 and Aranesp[®] in healthy volunteers.
 
Objectives:
 
 1. To evaluate and compare the key pharmacokinetic parameters of darbepoetin alfa in the serum after repeated-dose intravenous injections of 1 µg/kg BCD-066 (JSC BIOCAD, Russia) and 1 µg/kg Aranesp[®] (Amgen Europe B.V., the Netherlands) in healthy volunteers. 2. To evaluate and compare the key hemoglobin-based pharmacodynamic parameters after repeated-dose intravenous injections of 1 µg/kg BCD-066 (JSC BIOCAD, Russia) and 1 µg/kg Aranesp[®] (Amgen Europe B.V., the Netherlands) in healthy volunteers. 3. To evaluate and compare the safety and tolerability characteristics after repeated-dose intravenous injections of 1 µg/kg BCD-066 (JSC BIOCAD, Russia) and 1 µg/kg Aranesp[®] (Amgen Europe B.V., the Netherlands) in healthy volunteers.

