	
 • Visit 7 (Day 11): 240 h after the first injection (3 days after the second injection). • Visit 8 (Day 13): 288 h after the first injection (5 days after the second injection). • Visit 9 (Day 15): 336 h after the first injection (immediately before the third injection). • Visit 10 (Day 16): 360 h after the first injection (one day after the third injection). • Visit 11 (Day 18): 408 h after the first injection (3 days after the third injection). • Visit 12 (Day 20): 432 h after the first injection (5 days after the third injection). • Visit 13 (Day 22 – Day 23): 504 h after the first injection (immediately before the fourth injection); 528 h after the first injection (one day after the fourth injection). • Visit 15 (Day 25): 576 h after the first injection (3 days after the fourth injection). • Visit 16 (Day 29): 672 h after the first injection (7 days after the fourth injection). 
Safety monitoring procedures:
 
For safety evaluation, the study team will monitor vital signs (BP, pulse, respiration rate, and body temperature), perform regular physical examinations including assessment of the injection site, and run hematology and chemistry tests, blood tests for anti-darbepoetin alfa binding and neutralizing antibodies, urinalysis, and ECG.

Total Study Duration
	
Expected study duration is 2 years including up to 18 months of enrollment and 6 months of data collection and statistical processing.
 
Each study subject is expected to be in the study for 64 days, which includes the screening (14 days), administration of the test/reference drug and investigation of the PK and PD (29 days), and the follow-up period (Day 30 to Day 50).

PK Endpoints
	
 • Endpoints: 
 – The area under the Time vs. Concentration curve for darbepoetin alfa from injection to 72 h ($AUC_{(0-72)}$) after the first and the fourth IV injection of BCD-066 or Aranesp[®] – The maximum concentration of darbepoetin alfa in the serum after the first and the fourth IV injection of BCD-066 or Aranesp[®] (C_{max})

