Methods used to analyze PK and PD parameters

Descriptive statistics for the data on drug concentration in the serum, effect values, and protocol-specified PK and PD parameters will be performed using the following: mean values, geometric mean values, standard deviations, medians, upper and lower quartiles, min and max, and the coefficient of variation.

The statistical comparison involves the calculation of two-sided parametric 90% confidence intervals (CIs) for the ratios of the AUEC₍₁₋₂₉₎ means for hemoglobin and darbepoetin alfa following the IV injection of BCD-066 and Aranesp[®], and comparison of these CIs with the PD equivalence interval:

AUEC₍₁₋₂₉₎: [0.8; 1.25] (80-125%).

The study drugs will be considered equivalent if the estimated 90% CIs for the mean AUEC₍₁₋₂₉₎ ratio for darbepoetin in BCD-066 and darbepoetin in Aranesp[®] will fall in the said range.

Methods used to analyze the safety and demographic data

The interval (quantitative) data will be presented as mean values, standard deviations, medians, upper and lower quartiles, min and max. The normality of the interval data will be tested with the Shapiro-Wilk test.

The categorical (qualitative) data will be presented as the absolute and relative (proportions or percentages) number of observations.

The normally distributed interval data will be compared using the ANOVA and *t*-test for dependent and independent samples. Non-normally distributed interval data will be analyzed using non-parametric tests: Friedman's ANOVA, Kruskal-Wallis H test, Wilcoxon T test, and Mann-Whitney test. Categorical data will be compared using the χ^2 test or the Fisher's exact test.

Correction for multiple comparisons will be performed with the Benjamini-Yekutieli procedure.

Statistical methods will be chosen based on the type and distribution of raw data. Applicability of certain statistical tests will be evaluated after all the data are collected because it is impossible to predict the distribution pattern, data homogeneity and other data characteristics in advance.

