## 2. GOALS AND OBJECTIVES

### 2.1. Purpose

To confirm the equivalent pharmacokinetics, pharmacodynamics, safety, and tolerability of multiple IV injections of BCD-066 and Aranesp® in healthy volunteers.

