### **Categorical Data.**

The following categorical data will be analyzed in the study:

Safety:

- Rate and severity grades of AEs/SAEs
- Rate of Grade 3-4 AEs,
- Incidence of administration site reactions.
- Frequency of local reactions (total and by skin disorder type).
- Frequency of early withdrawals due to AEs.

Categorical data will be processed using frequency tables, contingency tables, the Fisher's exact test, the test of equal frequencies, Pearson's  $\chi^2$  test, and the Cochran-Mantel-Haenszel test. Percentages or proportions will be used to describe categorical data. The Benjamini-Yekutieli correction for multiple testing will be used. Statistical methods will be chosen according to the

type of initial data and their distribution. Appropriate statistical tests will be established after the data collection has been completed because the type of data distribution, sample homogeneity, etc. are unknown before the study start. For appropriate data processing, the list of statistical methods used may expand during the analysis.

Descriptive statistics for the data on drug concentration in the serum, effect values, and protocol-specified PK and PD parameters will be performed using the following: mean values, geometric mean values, standard deviations, medians, upper and lower quartiles, min and max, and the coefficient of variation.

The statistical comparison involves the calculation of two-sided parametric 90% confidence intervals (CIs) for the ratios of the  $AUEC_{(1-29)}$  means for hemoglobin and darbepoetin alfa following the IV injection of BCD-066 and Aranesp®, and comparison of these CIs with the PD equivalence interval:  $AUEC_{(1-29)}$  80-125%.

The study drugs will be considered equivalent if the estimated 90% CIs for the mean  $AUEC_{(1-29)}$  ratio for darbepoetin in BCD-066 and darbepoetin in Aranesp® will fall in the said range.

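### The trial sets out to confirm equivalent PK, but its only equivalence rule is an ambiguously worded one for AUEC(1-29): Cmax has no criterion on any reading, and AUC(0-72) has none on one reading

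*Protocol*

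**What the plan says.** **Purpose.** The protocol (Study Purpose and Objectives) states: "The purpose of the study is to confirm the equivalent pharmacokinetics, pharmacodynamics, safety, and tolerability". SAP 2.1 agrees: "To confirm the equivalent pharmacokinetics, pharmacodynamics, safety, and tolerability of multiple IV injections". The PK objective under it, in both documents, is only to evaluate and compare.

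**PK endpoints.** The protocol (PK Endpoints) lists AUC(0-72) and Cmax, each "after the first and the fourth IV injection of BCD-066 or Aranesp". SAP 4.1 and 8.4 do the same. None is ranked as primary or secondary.

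**Equivalence criterion.** There is one, in the protocol under Methods used to analyze PK and PD parameters, repeated in SAP 8.2 after the categorical-data text. It has three parts:
- A 90% CI for the ratio of AUEC(1-29) "means for hemoglobin and darbepoetin alfa following the IV injection of BCD-066" and the reference product.
- A "comparison of these CIs with the PD equivalence interval" of 80-125%, attached to AUEC(1-29).
- The decision sentence, "The study drugs will be considered equivalent if the estimated 90% CIs for the mean" AUEC(1-29) "ratio for darbepoetin in BCD-066 and darbepoetin in Aranesp" fall in that range.

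**Other treatment of PK.** Both documents plan descriptive statistics. SAP 8.4 gives formulas. SAP 8.2 (Quantitative Data) lists PK variables among those given two-sided tests at 0.05. SAP 9 plans no additional analyses, and SAP 10 declares no deviation from the protocol.

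**The concern.** AUEC(1-29) is defined only as an effect area (protocol PD Endpoints; SAP 4.2 and 8.4), so a ratio of it for darbepoetin does not correspond to any defined parameter. The stated purpose includes PK equivalence, but no rule names a PK parameter.

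The trial's headline conclusion could therefore be reached with no equivalence test of Cmax, and possibly none of AUC(0-72). Whether PK counts, after which injection and against which margin would be left to be settled once results are known. The SAP also says that "the list of statistical methods used may expand during the analysis", although that sentence closes the categorical-data paragraph and its reach to PK is arguable.

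**Working it through.** **1. What the rule covers.** There are four main PK comparisons: AUC(0-72) and Cmax, each after injections 1 and 4.

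| Reading of the rule | Hb AUEC(1-29) | AUC(0-72) | Cmax |
|---|---|---|---|
| (a) darbepoetin is a slip for a darbepoetin AUC, tested beside hemoglobin | covered | covered only if this is the AUC meant; injection not stated | no criterion |
| (b) the words mean the hemoglobin response to each product | covered | no criterion | no criterion |

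Under (a) the AUC itself is not identified. The protocol labels the area to infinity as 0-168 and the SAP labels it 0-∞, so AUC(0-72) is not the only candidate.

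The difference tests in SAP 8.2 do not fill the gap. No text treats a non-significant result as similarity, and such a test could not support that.

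**2. The plan's own power figure.** Inputs from SAP 6: CV = 12.92/45.4 = 28.46%, true ratio 1, 28 per arm, alpha 5%; limits 0.80-1.25 from the decision rule. On the log scale, SD = √ln(1+CV²), SE = SD·√(2/28), df = 54. Exact power of the two one-sided tests, integrated over the distribution of the pooled variance, is 80.96% against 80.95% stated. At 27 per arm it is 79.0%, so 28 per arm is the smallest size reaching 80%. The sample size is right for hemoglobin AUEC alone.

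**3. If PK is supportive.** The documents give no PK CV, so 25% is assumed, with a range of 20-30%. The 90% CI centred on 1 is exp(± t(0.95; 54) × SD × √(2/28)), with t = 1.674. At CV 25%, SD = √ln(1.0625) = 0.246 and the half-width is 1.674 × 0.246 × 0.267 = 0.110, giving 90-112%. At CV 20% it is 92-109%, and at CV 30% it is 88-114%.

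**4. If PK is decisive.** All named tests must pass, so alpha needs no adjustment but power falls. Assumptions: true ratio 1, 28 per arm, limits 80-125%, hemoglobin AUEC independent of PK. Independent PK tests multiply; for PK correlation 0.8, joint PK power was simulated with correlated means and variances. Overall success = joint PK power × 80.95%.

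| PK CV | One PK test alone | Hb + 2 PK tests: independent / corr. 0.8 | Hb + 4 PK tests: independent / corr. 0.8 |
|---|---|---|---|
| 20% | 98.8% | 79% / 79% | 77% / 79% |
| 25% | 91.1% | 67% / 70% | 56% / 66% |
| 30% | 75.5% | 46% / 53% | 26% / 44% |

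For example, at CV 25% with two independent tests: 0.911² × 0.8095 = 0.67. With hemoglobin plus one darbepoetin AUC, as in reading (a): 0.911 × 0.8095 = 0.74.

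**5. Sample size to restore 80% overall at PK CV 25%.** Two PK tests need 33 per arm (80.4% if independent, 82.0% at correlation 0.8). Four need 36 if independent (80.7%) or 34 at correlation 0.8 (81.0%).

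**The case against.** The best counter-argument is that this is a PD-primary trial with supportive PK. Hemoglobin AUEC(1-29) is the only endpoint called primary, the sample size rests on it alone, and the margin is labelled a PD margin. The purpose sentence also claims equivalent safety and tolerability, for which nobody would expect an 80-125% margin, so equivalent may be a general aim there. On this view the defect is one badly worded sentence and an over-broad claim; the powered test is intact.

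That intent is plausible, but neither document states it. The purpose says more, and the decision sentence speaks of the drugs being equivalent, not of equivalent PD. If PK is supportive, the plan must say so and the conclusion must be narrowed.

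Three lesser points stand:
- The sentence on expanding the methods concerns the choice of tests by data type. The finding does not need it.
- The power figures measure the cost of one remedy, not the defect, and they span 26% to 79% over the assumed CVs and correlations.
- Taking hemoglobin as independent of PK is a simplification. With PK correlation 0.8 and an assumed PK-hemoglobin correlation of 0.3-0.5, success at CV 25% would be about 71-72% with two PK tests and 66-68% with four, little above the table.

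**Conclusion.** The concern holds and must be fixed. The only decision rule is wrong as worded, because it applies an effect area to darbepoetin. None of the four PK comparisons has a criterion on reading (b). On reading (a) one unnamed darbepoetin AUC has one and Cmax has none. This follows from the text and depends on no assumed figure.

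The cost of making PK decisive does rest on assumptions: PK CV 25% (range 20-30%), true ratio 1 and hemoglobin independent of PK. Under these, the present sample gives 67-70% overall success with one injection tested and 56-66% with both, against about 81% for hemoglobin alone.

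**What to change.** Amend the protocol's PK and PD methods text and SAP 8.2 in the same words:

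1. State the rule as the 90% CI for the BCD-066/Aranesp ratio of hemoglobin AUEC(1-29) lying within 80-125%. Clarify what darbepoetin alfa was meant to cover; if a PK area, name it correctly, for example AUC(0-72).
2. Pre-specify 90% CIs of the geometric mean ratio, on the log scale, for AUC(0-72) and Cmax. Name the injection or injections that count and the margin, for example the 80-125% already in use. If PK is supportive, that margin is a reference range on which no decision hangs. Do not offer the two-sided difference tests as evidence of PK similarity.
3. State the role of PK before unblinding. If supportive, limit the formal equivalence conclusion to PD. If decisive, require every named test to pass and restate the joint power with a justified PK CV.

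The planned samples already supply the data, so items 1 and 2 cost only wording. Supportive PK costs no power but narrows the claim. Decisive PK would need about 33 per arm for one injection or 34-36 for both to restore 80% at an assumed CV of 25%.

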	
The PD analysis will include all subjects who have received all doses of the test/reference drug as per protocol.
 
Not more than 3 PD blood collections can be missed over the entire study. Subjects who have two consecutive blood samples missed will be not included in the analysis.
 
The PD analysis will be based on the hemoglobin concentrations, reticulocyte and RBC counts, and hematocrit. The limiting hemoglobin level in this study is 180 g/L. If the subject reaches this level before the last injection of darbepoetin alfa, he will be withdrawn from the study. If the subject reaches the limiting Hb concentration after he receives the last (fourth) injection of darbepoetin alfa, he will not be withdrawn from the study.

Safety Assessment
	
Endpoints:
 
 • The proportion of subjects who developed AE(s) after receiving at one injection of darbepoetin alfa • The rate of SAEs • The rate of CTCAE grade 3/4 AEs • The rate of withdrawals due to AEs • The proportion of subjects who had injection site reactions • The proportion of subjects who had antibodies to darbepoetin alfa on Day 29. 
Methods used for safety assessment:
 
The safety analysis will include all subjects who have received at least one dose of the test/reference drug.
 
The safety will be analyzed based on the information about:
 
 – The reported AEs/SAEs, – Results of physical examinations with an assessment of the injection site, vital signs, and instrumental and laboratory test results (hematology and chemistry, blood testing for binding and neutralizing anti-darbepoetin alfa antibodies, and urinalysis).

Statistical Analysis
	
Determination of sample size
 
The sample size was determined using the variation coefficients for hemoglobin increase (Hb AUEC) obtained by Cheung, 2001¹. The estimated Type I error was 5% ($\alpha=0.05$) and Type II error was 20% ($\beta=0.2$), with the test power of 80%.
 
The sample size was calculated with the “sampleN.TOST” function of the “PowerTOST” package for R. The calculation used the CV values and the ratios of the mean Hb increases (AUEC). The study

¹ W.Cheung, N. Minton, K.Gunawardena. Pharmacokinetics and pharmacodynamics of epoetin alfa once weekly an three times weekly, 2001

should include 28 subjects per group and 6 subjects as backups to replace potential early withdrawals (62 volunteers total).

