### **8.2. Description of the Statistical Methods to be Employed**

#### **Quantitative Data**

The following quantitative data will be analyzed in the study:

Pharmacokinetics:

- Plasma concentration of drug,
- Area under plasma concentration curve,
- Time (e.g., maximum plasma concentration time, half-life)
- Elimination parameters (e.g. clearance, terminal rate constant)

Safety:

- RBC results,
- Blood chemistry results,
- Vital signs;
- ECG findings,
- Urea analysis results,
- Skin disorders size at the sites of venipuncture,

- Skin disorders lifetime at the sites of venipuncture.

Pharmacodynamics:

- Absolute reticulocyte count.
- Hb level.
- Area under effect curve «absolute reticulocyte count — time».
- Area under effect curve «Hb level — time».
- Time (e.g. the time of the maximum increase of absolute reticulocyte count vs. baseline). The

statistical analysis will include two-tailed hypothesis testing; the chosen significance level is 0.05. Quantitative variables will be tested for normality using the Shapiro-Wilk test.

Normally distributed quantitative variables will be tested using the two-sample Student's t-test, Welch's t-test, and ANOVA.

Non-normally distributed quantitative variables will be tested using the Mann-Whitney U-test, the Wilcoxon test, the Kruskal-Wallis test, and the Friedman test.

Normally distributed quantitative data will be described using the following descriptive statistics: mean, SD, CV, min, and max.

Non-normally distributed quantitative data will be described using the following descriptive statistics: median, quartiles, CV, min, and max.

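### The purpose claims equivalent safety, but safety has no margin or planned interval and is compared only by difference tests, with a Benjamini-Yekutieli correction that makes a real difference harder to flag

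*Protocol*

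**What the plan says.** **Purpose.** The Protocol synopsis (Study Purpose and Objectives) states: "The purpose of the study is to confirm the equivalent pharmacokinetics, pharmacodynamics, safety, and tolerability". SAP 2.1 and 2.2 repeat this. Objective 3, in both documents, is weaker: it speaks only of evaluating and comparing safety and tolerability.

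**Equivalence rule.** The one margin, 80-125%, and the one decision rule, a 90% confidence interval, apply to the AUEC(1-29) ratio (Protocol, Methods used to analyze PK and PD parameters; SAP 8.2). No safety endpoint has a margin, a planned between-arm interval or a power statement.

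**Safety comparisons.** Under the Protocol's safety and demographic methods: "Categorical data will be compared using the χ^2 test or the Fisher's exact test". Quantitative safety data get t-tests, ANOVA or rank tests. SAP 8.2 adds: "statistical analysis will include two-tailed hypothesis testing; the chosen significance level is 0.05".

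**Correction.** The Protocol sentence is "Correction for multiple comparisons will be performed with the Benjamini-Yekutieli procedure", placed under the safety and demographic heading. The SAP sentence is "The Benjamini-Yekutieli correction for multiple testing will be used", placed in 8.2 under Categorical Data, where every listed item is a safety item.

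**Family.** Neither document says which tests form the family. The SAP contents list a section 8.6 on multiplicity, but the body has only 8.4, which holds PK and PD formulas, and then goes to 8.7. The Protocol lists six safety endpoints; SAP 4.3 lists five, without the overall proportion of subjects with adverse events.

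**The concern.** A test for a difference and a demonstration of equivalence answer different questions. Failing to reject equality with about 28 subjects per arm shows little, because moderate differences would usually go undetected. To support a claim of equivalent safety one needs a margin, or at least an interval showing which differences the data exclude. Neither is planned.

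The correction adds to this. Benjamini-Yekutieli limits false claims of a difference. Where the stated aim is to show that two products are alike, the error that matters more is missing a difference, and the correction makes that error more likely as the family grows. Because the family is undefined and SAP 8.2 leaves the choice of tests until after data collection, the strength of the correction is also open.

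At stake is what the study report may say about safety. The primary PD conclusion is not involved.

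**Working it through.** **The plan's own figure.** SAP section 6 gives N = 56 with 80.95% power for Hb AUEC, from CV = 12.92/45.4 = 28.46% and a true ratio of 1. On the log scale σ = √ln(1 + 0.2846²) = 0.279, and the standard error at 28 per arm is 0.279 × √(2/28) = 0.0746. Exact power for two one-sided 5% tests against 0.80-1.25 with 54 degrees of freedom is 80.95%; N = 54 gives 79.0%. The figure reproduces. It says nothing about safety, for which no figure is given.

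**Inputs for the safety check**
- Arm size: 28 (SAP section 6), or up to 31 if all 62 are dosed, since the safety set is everyone with at least one dose.
- Significance level: two-sided 0.05 (SAP 8.2).
- Family size m: 5 (SAP 4.3) or 6 (Protocol, Safety Assessment). This is an assumption, because the family is not defined.
- Event rates: assumed, because the documents give none.

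**Thresholds.** The i-th smallest p-value is compared with 0.05·i/(m·c), where c = 1 + 1/2 + … + 1/m.
- m = 5: c = 2.283; smallest p must be ≤ 0.05/(5 × 2.283) = 0.0044.
- m = 6: c = 2.45; smallest p must be ≤ 0.05/(6 × 2.45) = 0.0034. Even the largest must be ≤ 0.05/2.45 = 0.0204.
- m = 20 (if laboratory tests are counted): smallest p must be ≤ 0.0007.

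**Events needed against 0/28.** With equal arms, the two-sided Fisher p for k/28 versus 0/28 is 2·C(28,k)/C(56,k).

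| k | p | Significant at |
|---|---|---|
| 5 | 0.051 | none |
| 6 | 0.023 | uncorrected 0.05 |
| 7 | 0.010 | uncorrected 0.05 |
| 8 | 0.00438 | also m = 5 (limit 0.00438, only just) |
| 9 | 0.0018 | also m = 6 |

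So 6/28 (21%) is flagged uncorrected; 8/28 (29%) is needed with five endpoints, 9/28 (32%) with six, and 11/28 with twenty. At 31 per arm the counts are 6 uncorrected and 9 for either five or six endpoints.

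**Power.** Sum the two binomial probabilities over all tables whose Fisher p is at or below the threshold; 28 per arm, one differing endpoint, smallest-p threshold.

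| True rates | Uncorrected | m = 5 | m = 6 |
|---|---|---|---|
| 10% vs 30% | 33% | 10% | 7% |
| 10% vs 40% | 66% | 32% | 27% |
| 20% vs 60% | 82% | 50% | 48% |

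A simulation of the full step-up procedure (40,000 runs, independent endpoints, the others at 10% in both arms) agrees: 31.8% and 27.1% for 10% versus 40%. At 31 per arm that row reads 73%, 35% and 32%.

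**Several endpoints differing.** By the same simulation with m = 6 and 10% versus 40%, per-endpoint power is 34% if three endpoints differ and 42% if all six do, against 66% uncorrected.

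**What an interval would show.** At 20% in each arm, the 95% half-width is 1.96 × √(2 × 0.2 × 0.8/28) = 0.21, or 21 points. Zero events in 28 leaves a true rate of up to 1 − 0.025^(1/28) = 12.3% compatible with the data.

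**The case against.** A reader might infer that the sponsor plans to read a non-significant corrected safety test as proof of equivalent safety. The documents do not say so: the decision rule uses AUEC(1-29) only, and objective 3 claims no more than a comparison. That objection stands. The fault is a purpose that no planned safety analysis can support, rather than a stated plan to misuse a p-value.

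A reader might also infer that the corrected p-value would be the only safety evidence, or that the correction hides data. It does not. Both documents plan counts or percentages, so 8/28 against 0/28 would be visible, and anyone could compute an interval. What is missing is the planned interval itself.

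Nor is the correction the main cause of low sensitivity. Uncorrected power for 10% versus 30% is only 33%, because the trial was sized for Hb AUEC. Deleting the correction would not enable the trial to confirm equivalent safety.

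The power losses also depend on assumed rates and family size, and are largest when only one endpoint differs. The safety endpoints overlap (a grade 3/4 event is also an adverse event), so differences may occur together and the loss would then be smaller.

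Finally, many laboratory, ECG and vital-sign tests are planned, and false-discovery control is a recognised way to limit chance signals among them. This is a fair reason to keep a correction there, but not for the few categorical endpoints that carry the safety comparison.

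**Conclusion.** The point holds in this form. The purpose claims equivalence for safety and tolerability, while the plan provides no margin, no between-arm interval and no rule that could establish it. The difference tests cannot fill that gap, and the Benjamini-Yekutieli correction lowers their sensitivity further under every rate and family size tried. For 10% versus 40% with one differing endpoint, power falls from 66% to 32% (five endpoints) or 27% (six), and with all six differing to 42%. These sizes rest on assumed event rates, an assumed family and 28 per arm; the direction does not depend on them.

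Two stronger conclusions are not supported: that non-significance will be taken as equivalence, and that the correction is what makes the trial unable to judge safety. The matter is one of wording and reporting and is worth correcting. It leaves the primary PD analysis, its margin and N = 56 unchanged.

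**What to change.** 1. In the Protocol purpose and SAP 2.1 and 2.2, restrict the equivalence claim to what has a margin and rule, and say for safety and tolerability that they will be evaluated and compared, as objective 3 already does.
2. For the categorical safety endpoints, report per-arm counts and proportions and the risk difference with an unadjusted 95% confidence interval. Label p-values descriptive and drop the Benjamini-Yekutieli correction for these endpoints in both documents.
3. If the correction is kept for the many laboratory and vital-sign tests, define that family in advance and show uncorrected p-values beside corrected ones.
4. Use one list of safety endpoints in both documents.

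The cost is a wording change and standard output, with no added subjects, visits or samples. The downside is more chance findings among the safety comparisons, to be read as descriptive. The intervals will be wide, about ±21 points at 20% per arm, and will show plainly what a trial of this size can and cannot exclude.
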